#### **5. OBJECTIVES AND OUTCOME MEASURES**

**See Appendix C for schedule of procedures and visit windows**

**Research hypothesis:** To determine whether experimental treatment by injection with adalimumab will control the progression of early Dupuytren's disease more than control placebo treatment by injection with normal saline.

Part 1. Objectives	Outcome Measures	Timepoint(s) of evaluation of this outcome measure (if applicable)
Primary Objective To establish an effective dose of adalimumab for down regulating the myofibroblast phenotype in participants with Dupuytren's disease.	Expression of mRNA for $\alpha$ -SMA from participants on each treatment.	Analysis of tissue removed during surgery at 12-18 days post-treatment.
Secondary Objectives To determine the effectiveness of adalimumab for myofibroblast inhibition in participants with Dupuytren's disease and nodules.	For participants on each treatment 1. Expression of mRNA for COL-1A1, COL-3A1 and cadherin 11 2. Levels of $\alpha$ -SMA and collagen proteins. 3. Hardness of selected nodule 4. Ultrasound imaging of nodule size.	1 and 2. Analysis of tissue removed during surgery at 12-18 days post-treatment. Measures 3 and 4 measured before treatment and at 2 weeks post-treatment.
Monitor for adverse events	Adverse event assessment comparing active and placebo groups using visual inspection of injection site, surgery site and laboratory reports.	Observation at each research visit. Injection site assessment immediately after injection and 2

		weeks later. Health check phone call 1 week post treatment. Surgery site assessment at 2 weeks post-surgery.
To assess whether adalimumab affects the healing of the surgical incisions or subsequent scarring.	Visual assessment of surgical wounds using hand photographs of all participants on each treatment.	2 and 4 weeks post surgery.
Tertiary Objectives To determine circulating levels of adalimumab and antibodies to adalimumab in the blood.	Circulating levels of adalimumab and antibodies to adalimumab in the blood.	Analysis of blood samples taken pre-injection and at 2 weeks post-treatment.

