### Part 1. Dose response

For the dose response, study participants will be recruited with **established DD** who are scheduled for surgery for excision of the diseased tissue to correct flexion deformities of the fingers, to assess the efficacy of adalimumab in down regulating the phenotype of myofibroblasts. A maximum of 40 participants will be randomised to participate in the study if they meet the inclusion criteria and provide written consent. All participants will be screened for TB, Hepatitis B and C and HIV. If results are positive for any test, the participant will not be eligible to enter the trial and will be informed and counseled about the result of their test. Consented participants will enter the trial and receive the injection(s) two weeks prior to the scheduled surgery date. Intra-nodular injections will be delivered into the most prominent nodule due to be excised by surgery. If participants do not proceed to surgery at 12-18 days following injection, the reason will be recorded and they will continue with normal care. These participants may be replaced if still during the recruitment phase of the dose response study.

The diseased tissue excised during surgery, which would normally be discarded as waste, will be collected and analysed centrally for  $\alpha$ -SMA, COL-1A1, COL-3A1 and cadherin 11 mRNA expression, and  $\alpha$ -SMA and, where sufficient material exists, collagen protein levels. As other markers and assays of myofibroblasts become available these may also be used. The primary outcome measure will be mRNA for  $\alpha$ -SMA measured using RT-PCR for doses of adalimumab compared to equivalent volumes of saline.

Study participants will be seen at 4 time points after screening: week 0, week 2, week 2 post-surgery and week 12 post-surgery according to the summary chart (Appendix A). The schedule, duration of each visit and visit window is detailed in the Schedule of procedures (Appendix C: Schedule of procedures Part 1).

The safety profile of adalimumab is well known; with the most common adverse reactions being mild injection site reactions (see Section 4 Background). Participant safety will be monitored for three months after surgery, and if more than one participant in a dose cohort has an unplanned admission to hospital or unplanned surgery related to the surgery for Dupuytren's disease of the affected digit, or if any participant experiences a SUSAR, we will refer for advice to the Safety Committee.

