Participants may withdraw from the study at any time and will continue normal NHS clinical care. Information collected up to the point of withdrawal may still be used. To monitor safety, if the participant withdraws after they have received the medication their medical notes may be reviewed for 3 months after the baseline visit. Samples donated by participants for research are difficult to destroy on request once samples are processed for storage. Participants will be informed that they will not be allowed to request their samples to be destroyed at a later date.

The first participants will be recruited to 15 mg (in 0.3 ml carrier) and 35 mg (in 0.7 ml carrier) intra-nodular adalimumab cohorts. Each of these cohorts will initially recruit eight participants, of which two participants in each cohort will be assigned to placebo. A further eight participants will be recruited to a 40 mg (in 0.4 ml carrier) intra-nodular adalimumab cohort, with two participants in this cohort assigned to placebo.

Interim analyses of the excised disease tissue may be used to guide further decisions on cohort size and dose selection. However, the frequency of interim analyses is limited by the necessity for samples to be compared within each analysis run. The Trial Management Group (TMG) will monitor recruitment and will recommend the points at which any interim analyses will be performed.

Blinded data from interim analyses, together with safety data, will be presented to the Safety Committee for a decision on how best to proceed with the study. All decisions on cohort size and dose selection will be documented in the TMF. The Safety Committee may recommend to stop the dose response study at this point, to increase the participant numbers (either for all or specific cohorts), or to collect data at (an)other dose(s). Decisions on dose cohorts will adhere to the following rules:

- A maximum of 40 participants will be recruited
- The dose administered into the nodule will not exceed 80 mg adalimumab or 0.8 ml in volume.

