#### **Part 1**

Descriptive statistics will be used to describe the demographics between the intervention groups for each dose. This difference in the mean between cases and controls will be reported with 95% confidence intervals for all continuous outcome variables. P-values will be reported to 3 decimal places.

The primary outcome measure for [Part 1](#) is expression of mRNA for  $\alpha$ -SMA. Expression will be quantified with PCR using the standard curve method using GAPDH, B2M and PGK1 as housekeeping genes to normalise the samples.

The secondary outcome measures to be analysed include expression of mRNA for COL-1A1, COL-3A1, adherin 11 and levels of  $\alpha$ -SMA and collagen proteins, nodule size and nodule hardness.

For continuous variables, the difference in the means and the corresponding 95% confidence interval will be reported for each dose group and overall. For categorical variables, the number (and percentage) of participants in each category will be reported for each dose group and overall.

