### **11.3. The Number of Participants**

Based on our *in vitro* findings for the primary outcome measure ( $\alpha$ -SMA expression  $1.03 \pm 0.18$  in controls compared to  $0.55 \pm 0.11$  on treatment with anti-TNF), we estimate that, for **Part 1**, we will need 6 participants at each dose. As the *in-vivo* response is completely unknown a minimum of 8 participants will

be recruited at each dose randomised in a 3:1 ratio to adalimumab or placebo. Consenting participants who do not proceed to surgery will ideally be replaced. A maximum of 40 participants will be randomised.

For **Part 2**, the sample size is based on figures shown in Table 2. In our ultrasound trial (REC Ref. 11/SC/0447) there were 25 participants with mean  $53\pm 8$  for cases and  $32\pm 3$  for corresponding controls matched by age and sex. A minimum of 138 participants (69 per arm) are required to detect a moderate effect size of 0.62, based on a 5 point change in nodule hardness at 12 months and assuming a standard deviation of 8, 5% significance (2-sided) and 90% power, allowing for a 20% loss to follow up). These assumptions will be reviewed at the end of Part 1.

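### Part 1 leaves the scale, variance assumption and placebo comparator of its per-dose intervals open; with about two placebo participants per dose, coverage is unreliable or the intervals are needlessly wide

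*Protocol*

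**What the plan says.** Protocol 11.2 (Part 1) gives the analysis of continuous outcomes in one sentence: "the difference in the means and the corresponding 95% confidence interval will be reported for each dose group and overall". For the primary outcome, α-SMA mRNA, "Expression will be quantified with PCR using the standard curve method", normalised to housekeeping genes.

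The comparator comes from Protocol section 6 (Part 1), where expression is assessed "for doses of adalimumab compared to equivalent volumes of saline". The volumes differ by cohort: 0.3 ml (15 mg), 0.7 ml (35 mg) and 0.4 ml (40 mg). For the first two cohorts, "Each of these cohorts will initially recruit eight participants, of which two participants in each cohort will be assigned to placebo". The 40 mg cohort also has eight participants, "with two participants in this cohort assigned to placebo". Protocol 8.4 randomises 1:3 within each dose cohort. Cohorts may grow, up to 40 participants in all.

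Protocol 11.2 names no interval method, log scale or rule on sharing placebo for Part 1. Its log-transformation rule is written under Part 2. The current SAP is limited to Part 2 (SAP 1.2 and 2.1), and its Appendix 2 repeats the protocol's Part 1 outline.

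For nodule hardness and nodule size, Protocol section 5 states: "Measures 3 and 4 measured before treatment and at 2 weeks post-treatment". Protocol 11.2 does not say that the pre-injection value enters the Part 1 analysis.

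**The concern.** Read together, these sections imply six active against two volume-matched placebo participants at each dose, as an unadjusted difference in means on the raw expression scale. The only variability figures, in Protocol 11.3, are larger for controls than for treated samples, so the more variable arm would be the one with two people. The analyst must then choose between a pooled-variance and an unequal-variance interval without guidance, and the two behave very differently at these sample sizes. Three cohorts supply six placebo participants, yet each dose would use only two.

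Part 1's primary objective is to establish an effective dose, and section 6 allows interim tissue results to guide cohort size and dose selection within Part 1. The per-dose estimates are therefore what a reader would look at.

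**Working it through.** **Inputs.** Protocol 11.3: control 1.03 ± 0.18, treated 0.55 ± 0.11, difference 0.48. Protocol section 6: three cohorts of 6 active and 2 placebo. Two-sided 5% is assumed for Part 1. The ± values are read as SDs, which 11.3 does not state.

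**The plan's own figure.** Protocol 11.3 says "we will need 6 participants at each dose" but gives no power, so the figure cannot be confirmed. For 2 v 6 at SD 0.18, 0.48/(0.18 × √(1/2 + 1/6)) = 3.27, and 3.27 − 1.96 = 1.31, which is 90.4% power by the normal approximation (77.6% with a t distribution on 6 df). The figure is not shown to be wrong.

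**Pooled-variance interval, raw scale.**
- True SE: √(0.18²/2 + 0.11²/6) = 0.135.
- Pooled SD at the stated values: √((1 × 0.18² + 5 × 0.11²)/6) = 0.124.
- Pooled SE: 0.124 × √(1/2 + 1/6) = 0.102, about 25% too small, because five of the six degrees of freedom come from the less variable arm.

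**Welch interval, raw scale.** With variance terms 0.18²/2 = 0.0162 and 0.11²/6 = 0.0020, df = (0.0162 + 0.0020)²/(0.0162²/1 + 0.0020²/5) = 1.26. With the stated SDs plugged in, the half-width is 1.07.

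**Log scale.** The CVs are 0.18/1.03 = 17.5% and 0.11/0.55 = 20.0%. By √ln(1 + CV²), the log SDs are 0.173 and 0.198, nearly equal. The log effect is ln(1.03/0.55) = 0.63.

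**Simulation (300,000 replicates).**

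| Placebo v active | Interval | Coverage | Median half-width | Power |
|---|---|---|---|---|
| 2 v 6, raw, SDs 0.18 and 0.11 | pooled-t | 88.0% | 0.23 | 94% |
| same | Welch | 90.2% | 0.57 | 45% |
| 2 v 6, raw, both SDs 0.149 | pooled-t | 95.0% | 0.28 | 90% |
| 2 v 6, raw, both SDs 0.18 | pooled-t | 95.0% | 0.34 | 78% |
| 2 v 6, log | pooled-t | 96.1% | 0.37 (ratio ×/÷ 1.44) | 92% |
| 6 v 6, raw, shared placebo | Welch | 95.2% | 0.19 | over 99% |
| 6 v 6, log, shared placebo | pooled-t | 95.0% | 0.23 (ratio ×/÷ 1.26) | over 99% |

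Here 0.149 is the root mean square of 0.18 and 0.11. With equal SDs the Welch interval at 2 v 6 covers 92.4–92.6%.

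If both raw SDs are doubled (an assumption, since 11.3 calls the in vivo response unknown), 2 v 6 coverage stays at 88% pooled and 90% Welch. Power is then 51% and 27%, against 71% and 68% with shared placebo.

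**Half-width in SD units, three cohorts of 8.**
- Own placebo, each cohort alone (6 df): 2.447 × √(1/6 + 1/2) = 2.00.
- Own placebo, one residual variance over all cohorts (24 − 6 = 18 df): 2.101 × √(1/6 + 1/2) = 1.72.
- Shared placebo, four groups (24 − 4 = 20 df): 2.086 × √(1/6 + 1/6) = 1.20, which is 1 − 1.20/2.00 = 40% narrower.

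**The case against.** **Power.** A reader might infer that two controls per dose cannot show which dose works. The documents' figures do not support that. At the planning values the raw pooled-t interval excludes zero 94% of the time, although its under-coverage flatters that figure. The log-scale interval, still using only the cohort's own two placebos, has 92% power with 96% coverage. The 45% applies to Welch on the raw scale alone.

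**The planning values.** Protocol 11.3 does not label its ±, and the Fig 3 legend in section 4 reports related in vitro data as mean ± SEM from at least three patients. If these were SEMs with n = 3 (assumed), the SDs would be √3 = 1.73 times larger, the Welch half-width would be 0.57 × 1.73 = 0.99, and even 6 v 6 Welch power would be about 80%. Coverage depends on the ratio 0.18/0.11 = 1.6 and would not change if both scale alike. But that ratio is weak evidence of unequal variance from samples so small (F-test p = 0.54 at n = 3 per group). The under-coverage of the pooled interval is therefore conditional.

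**Reading of the text.** Own-cohort placebo is inferred; 11.2 does not rule out sharing. Two is only the initial number, and the overall estimate uses all placebo participants. An earlier SAP version may have settled these choices, but it is not among the documents. These points limit how firmly the defect can be stated. The current text still leaves the choices open.

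**Cost of sharing.** Volume-matched saline is a design choice. Section 4 says that loss of tension makes myofibroblasts disassemble their α-SMA fibres, so an effect of injected volume is not implausible. The 40 mg cohort is described as a further eight participants, so its controls may not be concurrent with the others. Two placebos per cohort can check this only weakly. This stands, and must be stated with the result.

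**Conclusion.** Part 1 does not specify scale, variance assumption or placebo comparator, and at these numbers the choice matters. On the natural reading, with the 11.3 figures taken as SDs, one raw-scale method misses the true difference about 12% of the time instead of 5%, and the other gives a typical half-width (0.57) larger than the planned effect (0.48) while still covering only about 90%. With equal SDs the pooled interval holds 95%. The log scale removes most of the coverage problem; a common variance and shared placebo supply the narrowing from 2.00 to 1.20 SD.

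The consequence is limited to Part 1's own conclusions. A reader might infer that the Part 2 dose is in doubt, but section 4 (IMP regime) bases that dose on other indications, not on these intervals.

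**What to change.** In Protocol 11.2 (Part 1), specify:

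1. Log relative expression in one linear model, with placebo shared across cohorts as one group, each dose as a group, and a common residual variance.
2. Samples compared within one assay run, or assay run as a model term. Section 6 already notes that samples need to be compared within a run.
3. Each dose reported as a ratio to shared placebo with a 95% CI.
4. The volume-matched comparison shown alongside, with a statement that sharing assumes no effect of saline volume or recruitment period and that two placebos per cohort can only weakly check this. Fitting that comparison with the common residual variance already narrows it from 2.00 to 1.72 SD.
5. ANCOVA for 2-week nodule hardness and nodule size, adjusting for the pre-injection value. No size is claimed, because the documents give no baseline-to-follow-up correlation.

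The cost is wording and the stated assumption in item 4; no new data are needed. SAP Appendix 2 only repeats the protocol's outline and would follow it. If Part 1 has already been analysed, report this as a labelled supplementary analysis.

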#### **8.4. Randomisation, blinding and code-breaking**

For Part 1 and Part 2, randomisation will be undertaken prior to or at the baseline visit prior to receiving the trial injection. The randomisation procedure and allocation ratios for the two parts of the trial will differ:

**Part 1:** participants will be randomised 1:3 to placebo or adalimumab within each dose cohort. Each participant will be assigned a Trial ID as they enter the study. Pharmacy will refer to the allocation log, which is securely stored in pharmacy, to ensure they dispense the IMP corresponding to the Trial ID. To enable unblinding, the randomisation will retrospectively be added to the RRAMP system (see below) by an unblinded member of the trial team.

**Part 2:** participants will be randomised 1:1 to placebo or adalimumab with stratification by age and centre. Participants will be randomised through a secure online service provided by the Oxford Clinical Trials Research Unit (OCTRUE) called RRAMP. RRAMP is used to randomise participants and this will generate a Trial ID and prompt an email to Pharmacy which informs them of which IMP (drug or placebo) to dispense.

The randomisation procedures will be fully documented, reviewed, tested and approved prior to the start of the study.

The methods for blinding will be influenced by the packaging of the adalimumab being used. Where possible the adalimumab will be supplied in a single use glass vial. However, a pre-filled syringe may be the only option if using the 40 mg in 0.4 ml formulation (see section 9.1).

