## 1.2 Changes from previous version of SAP

A summary of key changes from earlier versions of SAP, with particular relevance to protocol changes that have an impact on the design, definition, sample size, data quality/collection and analysis of the outcomes will be provided. Include protocol version number and date.

Version number Issue date	Author of this issue	Protocol Version & Issue date	Significant changes from previous version together with reasons
V1.0_30Nov2015	[name]	Protocol_V4.0_13Aug2015	Not applicable as this is the 1 st issue
V1.5_21Sep2016	[name]	Protocol_V8.0_19Aug2016	
Part 1 – dose choice: The choice of dose cohorts in Part 1 will be decided by the Safety Committee following analysis. No cohorts will use systemic injections.
 
Part 1 - secondary objectives:
 
Expression of collagen type I and <math>\alpha</math>-SMA protein in excised nodule tissue have been added.
 
Grip strength, range of motion, the Michigan Hand Outcomes Questionnaire (MHQ) and activity most restricted have been removed to reduce patient burden and encourage recruitment.
 
Part 1 – fewer study visits:
 
The study visit one week after injection will be replaced with a phone call. The study visits one and four weeks after surgery have been removed.
 
Inclusion/exclusion criteria – Updated in line with protocol.
 
Part 2 – dose choice: New formulation of adalimumab has been released (40mg in 0.4ml into the nodule) and therefore a new dose cohort was included.

V2.0_07Jan2021	[name]	Protocol_V13.0_21Nov2019	Restriction of analysis plan to include only RIDD part 2.

Repurposing anti-TNF for treating Dupuytren's disease (funded by Health Innovation Challenge Fund, Wellcome Trust)  
EudraCT Number: 2015-001780-40 and OCTRU Reference Number CTU0028

Version number Issue date	Author of this issue	Protocol Version & Issue date	Significant changes from previous version together with reasons

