## 11. APPENDIX 2: RIDD PART 1; STATISTICAL ANALYSIS OUTLINE (FROM PROTOCOL)

During the dose response (**Part 1**), analysis will be carried out using data from all participants randomised to **Part 1**.

Descriptive statistics will be used to describe the demographics between the intervention groups for each dose. This difference in the mean between cases and controls will be reported with 95% confidence intervals for all continuous outcome variables. *P*-values will be reported to 3 decimal places.

The primary outcome measure for **Part 1** is expression of mRNA for  $\alpha$ -SMA. Expression will be quantified with PCR using the standard curve method using GADPH, B2M and PGK1 as housekeeping genes to normalise the samples.

The secondary outcome measures to be analysed include expression of mRNA for COL-1A1, COL-3A1, aherin 11 and levels of  $\alpha$ -SMA and collagen proteins, nodule size and nodule hardness.

For continuous variables, the difference in the means and the corresponding 95% confidence interval will be reported for each dose group and overall. For categorical variables, the number (and percentage) of participants in each category will be reported for each dose group and overall.

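### The overall Part 1 difference has no dose-cohort term although randomisation is within cohort; a plain pooled interval would be too wide if cohorts differ

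*Protocol*

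**What the plan says.** Protocol 11.2, Part 1, states that for continuous variables "the difference in the means and the corresponding 95% confidence interval will be reported for each dose group and overall". SAP Appendix 2, which is headed as taken from the protocol, repeats it: "For continuous variables, the difference in the means and the corresponding 95% confidence interval will be reported for each dose group and overall". Neither names a model, stratum, weight or assay-run term for the overall figure. The current SAP adds no Part 1 method; its change log (SAP 1.2) records "Restriction of analysis plan to include only RIDD part 2".

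The design is stratified by cohort:

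- Protocol 8.4: "participants will be randomised 1:3 to placebo or adalimumab within each dose cohort".
- Protocol 6, Part 1, on the 15 mg and 35 mg cohorts: "Each of these cohorts will initially recruit eight participants, of which two participants in each cohort will be assigned to placebo". It continues: "A further eight participants will be recruited to a 40 mg (in 0.4 ml carrier) intra-nodular adalimumab cohort", again with two on placebo.
- The same section describes the primary outcome as measured "for doses of adalimumab compared to equivalent volumes of saline". The volumes are 0.3, 0.7 and 0.4 ml.
- On the assay, the same section says that "the frequency of interim analyses is limited by the necessity for samples to be compared within each analysis run".

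**The concern.** Cohort is the randomisation stratum. Cohorts differ in injected volume and partly in calendar time, and their tissue might be assayed in different runs. Any of these could shift the cohort mean in both arms.

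With a constant 3:1 ratio, such shifts cancel from the pooled difference in means. They stay in the residual variance, so the standard error overstates the uncertainty. The estimate itself is exposed only if the ratio drifts, which is possible because participants who do not proceed to surgery may, but need not, be replaced (Protocol 6 and 8.8).

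Each dose has only 6 active and 2 placebo participants. The overall contrast, 18 against 6 in the three initial cohorts, is therefore the most precise efficacy estimate in Part 1, and it is promised for the primary and all continuous secondary outcomes. An interval that is wider than necessary could obscure a modest reduction in α-SMA expression.

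**Working it through.** **Inputs from the documents.** Protocol 11.3 gives α-SMA expression of 1.03 (SD 0.18) in controls and 0.55 (SD 0.11) on anti-TNF, and states 6 participants per dose, raised to at least 8 at 3:1. The significance level is 5% (11.4).

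**Assumptions.** Two-sided testing; equal within-cohort SD σ; the same effect at every dose; normal cohort shifts with SD τ. The documents do not give τ, so it is varied.

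**1. The plan's own figure.**
- Difference: 1.03 − 0.55 = 0.48.
- Equal-weight SD: √[(0.18² + 0.11²)/2] = 0.149.
- Standardised effect: 0.48/0.149 ≈ 3.2.

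No Part 1 power is stated. At an assumed 90%, the normal approximation gives 2 placebo and 6 adalimumab at 3:1, or 3 + 3 at 1:1. Exact t power for 6 v 2 is 90.4%. The 6 per dose is reproduced under that assumption.

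**2. Why the pooled interval widens.** Take three cohorts of 6:2.
- With the ratio constant, the pooled and cohort-adjusted estimates are the same, with true standard error σ√(1/18 + 1/6) = 0.471σ.
- In the unadjusted analysis, cohort shifts add an expected (6 + 2) × 2 × τ² = 16τ² to the residual sum of squares on 22 degrees of freedom. The expected residual variance is σ² + (16/22)τ².
- The adjusted model keeps σ² on 20 degrees of freedom. The t critical value rises from 2.07 to 2.09.

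At τ = σ the formula gives √1.727 × 2.074/2.086 ≈ 1.31. This is a root-mean-square width ratio, so it lies slightly above the simulated ratio of mean widths (1.28).

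**3. Simulation** (60,000 trials per setting, σ = 0.149).

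| τ/σ | Mean half-width, pooled | Mean half-width, adjusted | Excess width | Coverage, pooled | Pooled power at 0.48 | Pooled power at 0.24 | Adjusted power at 0.24 |
|---|---|---|---|---|---|---|---|
| 0 | 0.144 | 0.145 | none | 95% | 100% | 90% | 90% |
| 0.5 | 0.156 | 0.145 | 8% | 96% | 100% | 87% | 90% |
| 1 | 0.186 | 0.145 | 28% | 98% | 99.9% | 75% | 90% |
| 2 | 0.271 | 0.145 | 87% | 99% | 95% | 43% | 90% |

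Excess width is pooled divided by adjusted, for example 0.186/0.145 = 1.28. The adjusted interval covers 95% throughout, and its power at 0.48 is about 100%. With five cohorts of 8 (the maximum of 40), τ = 2σ and an effect of 0.24, power is 61% pooled and 99% adjusted.

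**4. If the ratio drifts.** Take placebo counts of 2, 3 and 1, with cohorts kept at 8.
- The adjusted information is 6×2/8 + 5×3/8 + 7×1/8 = 4.25, against 18×6/24 = 4.5 unadjusted. With no cohort effect and an assumed effect of 1.3σ, power is 72% adjusted and 75% unadjusted.
- The unadjusted estimate now carries cohort shifts with weights 0, −0.222 and +0.222. At τ = σ its true standard error is √(0.2222 + 0.0988) = 0.57σ, against 1/√4.25 = 0.48σ adjusted.

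**The case against.** Several objections have force.

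- **The text is silent.** A reader might infer that the plan pools the cohorts as one sample. That is a natural reading of a difference in means, but a cohort-stratified difference also fits the wording, and the volume-matched comparator points towards one. Earlier SAP versions covered Part 1 and are not available here. What stands is that neither current document specifies a cohort term.
- **The loss is conditional.** A reader might infer that the interval is certainly wrong and that power is certainly lost. Both depend on a between-cohort SD that the documents do not give.
- **The run remark is limited.** Protocol 6 offers it as a reason to restrict interim analyses. It does not say that final data will come from several runs. Expression is also quantified against a standard curve and normalised to three housekeeping genes, and run has no bearing on nodule size or hardness. So run belongs in the model only for tissue assays, and only if there is more than one.
- **The error is conservative.** Pooled coverage is at or above 95% in every setting tested, including the drift example.
- **Power holds at the planning effect.** It is 95% or more up to τ = 2σ. However, Protocol 11.3 itself describes the in vivo response as wholly unknown, so smaller effects cannot be ruled out.
- **Little rests on the overall figure.** Part 1 is sized per dose, claims no power for the overall contrast, and does not determine the Part 2 dose, which Protocol 4 bases on other indications. This limits the importance of the point but does not remove it, because the overall interval is a promised result.

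**Conclusion.** The point holds as a low-cost improvement to the analysis. It is not an error that invalidates Part 1. The overall difference is specified without the stratum used for randomisation. If it is computed as a plain pooled difference and cohorts differ, its interval is about 8%, 28% and 87% too wide at between-cohort SDs of 0.5, 1 and 2 times the within-cohort SD. Power at the in vitro effect is almost unchanged up to 1 SD and 95% at 2 SD; at half that effect it drops materially from 1 SD upwards. With no cohort effect there is no loss.

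The documents do not support a claim of bias in the pooled estimate while the 3:1 ratio holds, nor any criticism of the per-dose intervals. The figures rest on an unknown between-cohort SD, a common within-cohort SD of 0.149 taken from in vitro data, and an equal effect at each dose.

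**What to change.** In Protocol 11.2, Part 1, and SAP Appendix 2, state that the overall adalimumab–placebo difference and its 95% confidence interval, for the primary and continuous secondary outcomes, come from a linear model with treatment and dose cohort as factors, and that the result averages over the doses studied. For tissue assay outcomes only, if samples are assayed in more than one run, add run as an additive factor. Do not use cohort-by-run cells: with two placebo participants per initial cohort, some cells could contain no placebo and would contribute nothing to the contrast.

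The cost is a sentence or two and, with three cohorts, two degrees of freedom; each additional run costs at most one more. If there is no cohort effect and the ratio holds, width and power are essentially unchanged (half-width 0.145 v 0.144; power 90% either way at an effect of 0.24). If there is no cohort effect and the ratio drifts, there is a small power loss, about 72% against 75% in the example above.
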